### **I. Hypotheses and Specific Aims:**

Every year, alcohol use disorder (AUD) generates millions of emergency department (ED) visits and hospital admissions, costing the U.S. health sector over \$90 billion. These hospital admissions are critical opportunities to start patients on addiction pharmacotherapy, but factors like medication non-adherence and post-discharge relapse contribute to frequent re-admissions. Two single-dose interventions are well suited to facilitate treatment retention and prevent re-admissions due to their prolonged, adherence-independent effects: extended-release (XR) naltrexone injection and intravenous (IV) ketamine infusion. These have not been thoroughly investigated in the hospital setting among high-utilizer, safety-net populations. Therefore, we aim to:

- 1. Test the feasibility of randomizing hospitalized patients (n=45-60, age 18-65) with multiple AUD-related admissions to treatment with either extended-release (XR) naltrexone, intravenous (IV) ketamine, or no single-dose medication, all with enhanced linkage to care.** Feasibility outcomes such as recruitment rate, patient acceptability, post-discharge follow-up rate, and adverse events will help to identify key lessons for a future comparative effectiveness study.
- 2. Estimate the 30-day re-admission rate for patients randomized to treatment with XR naltrexone, with IV ketamine, or no single-dose medication, all with enhanced linkage to care.** We hypothesize that the re-admission rate will be lower for each of the two single-dose medication groups than for the “linkage-alone” group.

### **II. Background and Significance:**

Alcohol use disorder (AUD) generates approximately 5 million U.S. emergency department visits every year, leading to 2 million hospital admissions and collectively costing the health sector over \$90 billion dollars annually. Because addiction treatment is seldom accessed, hospital admission represents a major opportunity for linkage to care and initiation of oral (PO) naltrexone, a first-line medication shown to improve outcomes such as number of drinking

days, drinks per day, and health care utilization. Denver Health (DH) provides a dedicated addiction consult service (ACS) to assist in these efforts, and the ACS sees hundreds of new consults per month. Yet alcohol-related admissions at DH – estimated at nearly 2,000 per year – show a higher 30-day re-admission rate than the hospital-wide average (Figure 1). This is consistent with a nationally reported re-admission rate for alcohol-related disorders of 21% compared to 14% overall in 2014, ranking it 4th among common diagnoses. Additionally, there is low post-discharge treatment engagement for these patients: one sample of hospitalized DH patients with AUD demonstrated an 11.8% follow-up rate at addiction clinic (chart review).

These sub-optimal transitions of care underscore the limited benefit of oral naltrexone for high-utilizer, safety-net populations who may have social contexts that compromise medication adherence. Different tools are needed that can facilitate post-discharge treatment engagement and reduce re-admissions, goals in line with the DH Center for Addiction Medicine (CAM) and upcoming Hospital Transformation Project application.

The following two pharmaceutical options are well-suited to the hospital setting and complementary to the myriad behavioral strategies to improve treatment compliance and linkage to care:

1. An extended-release (30-day, “XR”), intramuscular injection of naltrexone (Vivitrol®). Studies on XR naltrexone have shown better long-term medication continuation compared to oral naltrexone and reduced heavy drinking days compared with placebos. Additionally, one meta-analysis showed a trend toward fewer admissions compared to oral naltrexone. One ongoing clinical trial is directly comparing oral to XR naltrexone for AUD in a safety-net hospital in Boston, and it is expected to evaluate the results in late 2020. Regardless, data from multiple centers and regions are needed, and our study uniquely targets high-utilizer patients.
2. A single infusion of intravenous ketamine, a dissociative anesthetic used in general anesthesia and pain management. At sub-anesthetic doses, ketamine provides rapid effects on mood that extend weeks beyond administration, and in 2019 the FDA approved an intranasal formulation for treatment-resistant depression. For AUD, treatment with ketamine decreased cravings and drinking at 10 days post-infusion in a human laboratory study that excluded patients with depression. In a recent randomized trial, AUD patients were given one ketamine infusion and subsequently showed a higher rate of abstinence at 21 days beyond treatment and better attendance at the final study visit compared to the control group (100% vs 74%, respectively), with no serious adverse events reported.

Both single-dose interventions hold great potential for improving AUD post-hospital transitions and reducing immediate re-admissions, but more data on feasibility and effectiveness are needed.

### III. Preliminary Studies/Progress Report:

There have been no preliminary studies. However, an initial Tableau query showed that at Denver Health, patients admitted to the hospital with an alcohol related diagnosis had a 30-day readmission rate of between about 10 and 40 percent (see Figure 1). This is notably an underestimation, given that patients may have had readmissions at hospitals outside of Denver Health, which would not have been captured in those data.

There is also low outpatient treatment engagement following discharge for these patients. I reviewed a cohort of 17 patients that I cared for in August and September 2019, all of whom I referred to outpatient addiction clinic for treatment of alcohol use disorder. Only 2 presented within the following month. Among the 9 who were prescribed oral naltrexone, only 1 presented.

[figure not shown]

Figure 1 DH hospital re-admissions. Obtained via Tableau with assistance from [name]. Alcohol admissions based on All-Patients-Refined-Diagnosis-Related-Groups (APR-DRG) 775 and 280.

### IV. Research Methods

#### A. Outcome Measure(s):

See table 1 for primary and secondary outcomes. In brief, our primary outcomes will be those related to feasibility as well as risk of 30-day all-cause hospital re-admissions. Secondary outcomes include risk of 30-day all-cause emergency department visit,

differences in readiness-to-change, and likelihood of having an alcohol metabolite (EtG) in the urine at follow-up.

*Table 1 Primary and secondary outcomes*

	Study Aim	Description	Instrument(s)
1' feasibility outcomes	1	Recruitment rate (# enrolled / month), follow-up rate, patient acceptability, adverse effects	Chart review, questionnaires
1' clinical outcome	2	Risk of 30-day all-cause hospital re-admissions	Chart review
2' clinical outcomes	2	Risk of 30-day all-cause ED visits	Chart review
	2	Within-subject difference in readiness-to-change 	Questionnaire
	2	Laboratory(+) for alcohol at SUDS	Urine EtG
	2	Percent of binge drinking days  since discharge	Questionnaire

### **B. Description of Population to be Enrolled:**

See Table 2 and 3 for inclusion and exclusion criteria. Rationales are also listed.

*Table 2 Inclusion criteria*

	INCLUSION criteria	Rationale
	Age 18-65	Limiting study scope to adult patients
	1+ alcohol-related* admission(s) OR 2+ alcohol-related ED visits in past 12 mo.  *Admission diagnoses includes any of following: - alcohol use / intoxication - alcohol withdrawal - alcohol use disorder / dependence - seizure thought to be related to alcohol withdrawal - encephalopathy thought to be related to alcohol - pancreatitis thought to be related to alcohol - liver disease thought to be related to alcohol - cardiac arrhythmia or heart failure thought to be related to alcohol - gastrointestinal bleed thought to be related to alcohol	Limiting study scope to high-utilizer patients
	Has insurance (public or private)	Can follow-up at SUDS clinic
	Seen by addiction consult	Part of recruitment plan

*Table 3 Exclusion criteria*

	EXCLUSION criteria	Rationale
	Known or suspected active COVID-19 infection	Staff safety and ability to immediately follow up at SUDS clinic

	Hepatic: AST/ALT >5x upper-limit of normal, decompensated liver failure	Naltrexone can rarely cause hepatotoxicity. 5x ULN used by study by Collins et al (2015)
	Renal: Glomerular filtration rate <30ml/min	Naltrexone not recommended in renal failure
	Cardiovascular: History of acute coronary syndrome, cerebrovascular event, hypertensive crisis, known cardiomyopathy	Ketamine can transiently raise blood pressure
	Known elevated intracranial pressure	Ketamine can transiently raise blood pressure
	Thrombocytopenia (<50/microliter)	Naltrexone can potentially worsen thrombocytopenia
	Active moderate/severe withdrawal (based on hospital withdrawal protocol)	May need acute care that would interfere with intervention and discharge planning
	Active delirium (alcohol-related or otherwise)	Ketamine's dissociative effects could theoretically worsen delirium
	Already enrolled in study	A-priori decision to only enroll patients once
	XR naltrexone or IV ketamine in last 30 days	Prior administration could affect ability to distinguish effect of current intervention. Recent receipt of intervention would also be evidence that intervention not effective for them.
	Known intolerance to naltrexone or ketamine	Avoid harm to patient
	Other active severe substance use disorder (tobacco, cannabis excluded)	Limiting study scope to AUD
	Pregnant or breast-feeding, or planning.	Risk of harm to fetus not well established for naltrexone or ketamine
	Opioids: physical dependence or anticipated use in the next 30 days	Naltrexone is an opioid-antagonist
	Unstable psychiatric illness (active psychosis, active suicidality)	Ketamine's dissociative effects could worsen psychiatric decompensation
	Moving from region within 30-days of discharge	Cannot have immediate follow up at SUDS
	Discharge to acute/residential treatment	Cannot have immediate follow up at SUDS
	Involuntary hold	Cannot have immediate follow up at SUDS

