### ***Data Collection***

Data will be primarily collected at four time-points (Table 4). Data will be entered by staff into a REDCap database on tablet computers in the hospital and at SUDS clinic. Data collected at enrollment will primarily be descriptive, including demographics, recent drinking history, readiness to change, and various contributing factors to drinking. Immediately after intervention, vital signs,

symptoms, and acceptability will be recorded. Data collected on post-discharge arrival to SUDS clinic will include most 2' clinical outcomes. We will obtain re-admission rate (1' clinical outcome) through chart review, conducted by research team members at 30-days post-discharge.

Table 4 Patient flow and data collection points

Step	Who	Notes	Data collected – staff entered
Patient identified on consult list	ACS	Quick screen that meets inclusion criteria	
↓			
Addiction consult performed	ACS	Evaluation, withdrawal management, medication (though if patient consents to study, will not be prescribed an addiction medication at discharge), brief therapy, referrals, disease screening/harm reduction	
↓			
Screen, consent, randomization	ACS	Formal screen to identify any exclusion criteria. Simple randomization by algorithm	
 
• E-Consent (should include consent to see records in “care everywhere” – some hospitals require permission – when checking for ED visits and re-admissions)
 
• Screening documentation (inclusion and exclusion criteria)
 
• Alcohol-related admissions in last 12 months (date, location, top 3 diagnoses)
 
• Assigned group
 

↓			
Baseline data, referral to SUDS [data collection point #1]	ToD	ToD collects baseline data first, then performs “biopsychosocial intake” and sets up SUDS appointment within 1 week of discharge.  Discharge date is not always predictable;	
 
• Demographics
 
• Baseline clinical data
 
• Depression symptoms baseline (PHQ9 2 wks)
 
• Drinking History 7-days prior to admission (TLFB)
 
• Readiness to change (SOCRATES-8A)
 
• ACE Questionnaire
 

		ACS to review active hospitalized research participants and contact ToD/update date in RedCap as needed.	
↓			

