Intervention administered [data collection point #2]	RN, ACS	
For 'linkage-alone' group, data to be entered following consult.
 
For NTX group, intervention administered prior to discharge (could be same day as consent). Vitals immediately preceding and 40 min post- injection. Data collected after administration.
 
For KET group, intervention administered prior to discharge (could be same day as consent), though should have no food for at least 3 hours (~50% gastric emptying). Vitals immediately preceding, after completion, and 2 hours following end of intervention.
	
 
Vital signs (HR, BP, O2): linkage-alone group- baseline only, recorded after consult. NTX group- baseline, 40 min after administration. KET group- baseline, end of administration (~40min), 2 hours after end of administration.
 
Most recent AST, ALT
 
UDS-5 data
 
[for KET] Dissociative symptoms (CADSS) after administration (40 min)
 
[for NTX and KET] Acceptability of intervention (10-point Likert) after administration
 
[for NTX and KET] Readiness to change (SOCRATES-8A) after administration (40 min)
 
 
ORDER: CMP (if not already obtained), UDS-5 (if not already obtained)
 
ORDER in discharge orders (outpatient): CMP, UDS-5, urine EtG (if not already ordered)

↓			
Presentation to SUDS, data entered, contingency management reward administered [data collection point #3]	SUDS staff	
Upon presentation, staff to collect study data. After completion, will receive contingency management reward.
 
Then patient to complete standard intake/follow-up visit, if willing.
	
 
Drinking History since discharge (TLFB since discharge)
 
Depression symptoms (PHQ9 modified to read "since discharge.")
 
Readiness to change (SOCRATES-8A)
 
[for KET] Dissociative symptoms (CADSS)
 
Adverse Events (Modified PRISE)
 
Acceptability of intervention (10-point Likert)
 

		Staff to instruct patient to present to the clinic laboratory (e.g. pav G) for CMP after the visit.	
 
Contingency management feedback (10-point Likert, open ended)
 

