30-day chart review [data collection point #4]	Research staff	Should check encounters tab as well as “care everywhere” for Denver Metro region.	
 
Admissions (up to 5) within 30 days of discharge date (date, location, up to top 3 main diagnoses based on documentation available).
 
ED visits (up to 5) within 30 days of discharge date (date, location, up to top 3 main diagnoses based on documentation available).
 
AST, ALT obtained at SUDS f/u (if available)
 
Urine EtG obtained at SUDS f/u (if available)
 

Screening: The addiction consult team will attempt to screen patients meeting the inclusion criteria during inpatient admission. We anticipate 10 patients will meet inclusion criteria weekly. They will be assessed for clear exclusion criteria documented in the chart, and if none are noted the patient will be asked if they would like to join the study and complete the screening. If still no exclusion criteria are met and the patient expresses interest, they will be engaged in informed consent. The primary team will be notified by the addiction medicine team. Each combined process of screening and consent is anticipated to require 15 minutes at the end of a typical consultation. The screening window is anticipated to last 5 months.

Randomization: Patients will undergo a simple randomization algorithm to one of three arms.

Intervention:

- **Arm 1:** Receive a single dose of XR naltrexone (380mg) prior to discharge.
- **Arm 2:** Receive a single infusion of IV ketamine (0.5 mg/kg over 40 minutes) prior to discharge.
- **Arm 3:** No single-dose medication
- *All groups will receive enhanced linkage to care that includes contingency management, initiation of biopsychosocial intake, and appointment scheduling. This aspect alone surpasses the current standard of care.*

Contingency Management: Patients will receive a debit card prior to discharge from the hospital. We will utilize a pre-existing system - ClinCard by Greenphire. Participants will receive \$10 upon completion of baseline data, and \$20 upon completion of follow-up data (at SUDS clinic).

Follow up: Patients will be assigned a follow-up within 7 days of discharge at the outpatient addiction clinic (Denver Health SUDS clinic in pavilion K).

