#### **D. Description, Risks and Justification of Procedures and Data Collection Tools:**

*Table 5 Overview of risks and justifications of procedures and data collection tools*

Procedure/Tool	Description, Risks	Justification
Injection of IM medication (naltrexone)	Risks include minimal pain and discomfort at the injection site which will occur on the lateral thigh or the buttock. One study suggested that the discomfort of an injection itself deterred a large number of participants.  If that is the case for our study, this decision will be honored with no repercussion aside from not enrolling in the study. More serious risks such as infection, blood clot, bleeding and/or allergic reaction are rare.	These risks are justifiable as there is very little risk of serious or permanent harm, and potential benefits in terms of preventing the consequences of heavy drinking are almost certainly greater.
Medication-related risks of naltrexone	Risk of opioid withdrawal if the patient is taking opioids concurrently (an exclusion criteria); Liver injury can be seen, but is usually mild and self-limiting. Patients with AST/ALT >5x ULN, hepatic failure, or decompensated cirrhosis will be excluded. Nausea, sleepiness and headache are the other most common medication side effects.	These risks are justifiable as there is very little risk of serious or permanent harm, and potential benefits in terms of preventing the consequences of heavy drinking. It is a single dose which limits exposure.
Medication-related risks of ketamine	Risk of unpleasant dissociative symptoms, delirium, hallucinations; high blood pressure which could lead to adverse cardiac events if patients are not screened carefully; initiation of ketamine abuse after discharge.	These risks are justifiable as there is very little risk of serious or permanent harm, and potential benefits in terms of preventing the consequences of heavy drinking. It is a single dose which limits exposure. Patients who experienced delirium during hospital stay will be excluded. Patients with known cardiovascular disease will be excluded. The most recent randomized trial using ketamine found no initiation of ketamine “abuse” following administration. 

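### The platelet exclusion in Table 3 is missing a factor of 1,000: it is printed as fewer than 50 per microliter and presumably means fewer than 50 thousand

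*Combined protocol and SAP*

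**What the plan says.** Section IV.B, Table 3 lists the exclusion criteria with a reason for each. The platelet row reads "Thrombocytopenia (<50/microliter", and its reason is "Naltrexone can potentially worsen thrombocytopenia". Table 3 has two other laboratory cut-offs: AST/ALT above five times the upper limit of normal, and "Renal: Glomerular filtration rate <30ml/min".

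Section IV.C describes how the criteria are applied. On screening it says of patients who meet the inclusion criteria: "They will be assessed for clear exclusion criteria documented in the chart". Table 4, at the screening, consent and randomization step, has staff record "Screening documentation (inclusion and exclusion criteria". At data collection point #2, the study laboratory orders are "ORDER: CMP (if not already obtained), UDS-5 (if not already obtained".

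Section IV.D, Table 5 says of the intramuscular naltrexone injection: "More serious risks such as infection, blood clot, bleeding and/or allergic reaction are rare".

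**The concern.** A cut-off of 50 platelets per microliter is far below any count at which a patient could be considered for enrollment, so as written the row does nothing. The other two laboratory cut-offs in Table 3 work as printed.

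The row is an operative safety limit. Arm 1 is a single 380 mg extended-release injection, described in the Background as lasting 30 days, so it cannot be withdrawn once given. The population makes low platelets a realistic possibility. The qualifying diagnoses include alcohol-related liver disease and gastrointestinal bleeding, and the hepatic exclusion removes only decompensated failure or marked transaminase elevation. An eligibility or deviation check against the written text would pass a patient with 20,000 platelets per microliter, whom the presumed limit excludes.

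**Working it through.** **Inputs from the documents.** Printed limit: 50 per microliter (Table 3). Planned enrollment: 45 to 60 (Sections I and IV.C). Number of arms: three (Section IV.C). The plan gives no derivation of the limit, so there is no figure to reproduce; the check is one of units.

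**Inputs that are not in the documents.**
- The usual adult platelet count is taken as about 150,000 to 450,000 per microliter. This is general laboratory knowledge and is used only for scale.
- The share of otherwise eligible patients with counts from 50 to 49,999 per microliter is unknown. A range of 1% to 5% is assumed for illustration.

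**Step 1: convert the printed limit.** One liter is 10^6 microliters, so 50 x 10^6 = 5 x 10^7 per liter = 0.05 x 10^9/L.

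**Step 2: convert the presumed limit.** 50 x 10^3 per microliter = 50,000 per microliter = 50 x 10^9/L.

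**Step 3: ratio.** 50 / 0.05 = 1,000.

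**Step 4: compare each with usual counts.**
- Printed: 50 / 450,000 = 0.01% and 50 / 150,000 = 0.03% of a usual count. Essentially no patient falls below this.
- Presumed: 50,000 / 450,000 = 11% and 50,000 / 150,000 = 33% of a usual count. This is a workable limit for clinically important thrombocytopenia and fits the stated reason.

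**Step 5: who is treated differently.** Counts from 50 to 49,999 per microliter pass the printed rule and fail the presumed one.

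**Step 6: illustrative number of patients, literal reading.**
- Whole trial: 45 x 0.01 = 0.45, up to 60 x 0.05 = 3.0.
- Naltrexone arm: 45 / 3 = 15 and 60 / 3 = 20 people if the split is about equal (randomization is simple, so this is only the expected size). 15 x 0.01 = 0.15, up to 20 x 0.05 = 1.0.
- If screeners read the rule as 50 thousand, the number is 0.

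**Step 7: look for a correction elsewhere.** Thrombocytopenia is mentioned only in this Table 3 row. No other section gives a platelet threshold, a multiplier or a reporting unit. The screening text and Table 4 refer back to the criteria without restating them. The laboratory orders at data collection point #2 come after randomization and name no platelet count, so they do not supply the missing figure either.

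**The case against.** The strongest reply is that this is a typographical slip with no practical effect. Addiction consult clinicians carry out the screen after their own consultation, and they work with the primary team to order and give the drug. For harm to follow, all of them would have to accept a limit of 50 platelets per microliter. That is improbable, and nothing in the documents suggests that they would. This stands: the documents do not show that the safeguard would fail in practice.

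It can also be said that the 1% to 5% range has no source, and that the other exclusions would remove some low-platelet patients. This stands too. The patient counts only illustrate scale under the less likely reading; the factor of 1,000 is the only firm number.

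Third, the screening form is not in the documents and may already carry the right unit. So the most that can be said is that the error could carry over if the row is copied as printed.

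Last, a multiplier might have been lost when the PDF was converted to text. That cannot be fully excluded, but it is unlikely: the parenthesis is intact, there is no gap or stray character, and superscripts survive elsewhere in the text. The sponsor can settle it by looking at the source file.

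None of these points makes the printed limit usable. A protocol should not depend on its readers silently correcting a safety criterion.

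**Conclusion.** The point holds. The platelet limit is wrong as printed, by a factor of 1,000 relative to the only plausible intended value, and nothing else in the document corrects it. That the intended value is 50 x 10^3 per microliter is an inference, which the sponsor should confirm. The likely effect on who is enrolled is nil if clinicians read the limit as 50 thousand. A literal reading would let in about 0.45 to 3 patients in the whole trial and 0.15 to 1 in the naltrexone arm, under the assumed 1% to 5% range. It should be corrected because it is the protocol's only statement of this safeguard. It has no bearing on sample size, power, outcomes or analysis.

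**What to change.** Reword the Table 3 row as: Thrombocytopenia (platelets <50 x 10^3/microliter, i.e. 50,000/microliter or 50 x 10^9/L), after the sponsor has confirmed the value. Check that the screening documentation carries the same number and unit.

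The cost is a one-line edit in each place. Compared with the probable clinician reading, no patient's eligibility changes. Compared with a literal reading, a few patients would become ineligible, which is what the row is meant to achieve. Nothing in the design or the analysis has to change.
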